**Figure 1. Cohort Enrollment**

**Table 2. Study Assessments for Cohort 1**

	Screening	Treatment Period															Follow-Up	
Visit number	1	2	3	4	5	6	7	8	9	10	11	12	13	14	15	16	17	18
Time point (study day)	-14 to -1	0	1 (±1 h)	2 (±2 h)	5 p (±4 h)	7 (±6 h)	12 p (±6 h)	14 (±6 h)	19 p (±6 h)	21 (±6 h)	28 (±6 h)	29 (±1 h)	30 (±2 h)	33 (±4 h)	42 (±3 d)	56 (±5 d)	84 (±5 d)	112 or ET (±5 d)
Informed consent	X																	
Demographics/medical history	X																	
Inclusion/exclusion	X																	
Physical examination a	X	X				X		X		X	X				X	X	X	X
Vital signs b	X	X	X	X	X	X	X	X	X	X	X	X	X	X	X	X	X	X
Pulse oximetry c		X				X		X		X	X							
Clinical safety labs d	X	X				X		X		X	X			X	X	X	X	X
Pregnancy test e	X	X														X		X
Hepatitis and HIV screen	X																	
12-lead ECG f	X	X					X				X						X	
Tetanus and VZV antibodies g		X															X	X
PDAI		X				X		X		X	X			X	X	X	X	X
PK sampling h		X	X	X	X						X	X	X	X				
Immunogenicity i		X						X			X					X	X	X
Study drug administration j		X				X		X		X	X							
Immunoglobulins (IgG, IgA, IgM) and IgG subtypes (IgG1-4) k	X	X	X	X	X	X	X	X	X	X	X	X	X	X	X	X	X	X
CIC		X			X	X	X	X	X	X	X			X	X	X	X	X
Anti-Dsg (1 and 3) antibody titers	X	X				X		X						X		X	X	X
C3 and AECA l		X						X						X		X	X	X
FCGR2A by buccal swab m		X																
RNAseq		X						X						X		X	X	X
Urine IgG		X						X						X		X	X	X
Immunophenotyping n		X									X					X		
Exploratory pemphigus immune response biomarkers		X			X	X	X	X	X	X	X			X	X	X	X	X
Optional skin biopsy		X	X	X				X						X		X	X	
Photography o		X												X		X	X	X
Adverse events	To be collected from the date that the ICF is signed through the last study visit																	
Concomitant medications	To be collected from within 14 days prior to Day 0 through the last study visit																	

Abbreviations: CIC = circulating immune complexes; d = days; ECG = electrocardiogram; ET = early termination; h = hour(s); HIV = human immunodeficiency virus; ICF = informed consent form; PDAI = Pemphigus Disease Area Index; PK = pharmacokinetic; VZV = varicella zoster virus.

- a. Complete **physical examination**, including weight, to be performed. Height and BMI will be additional assessments conducted at screening.
- b. **Vital sign** measurements (sitting blood pressure, heart rate, respiratory rate, and oral temperature) to be obtained after 5 minutes of seated rest. Any abnormal measurements are to be repeated after 5 minutes of rest. On Days 0, 7, 14, 21, and 28, vital sign measurements will be collected immediately prior to the infusion; 15, 30, and 45 minutes after the start of the infusion; at completion of the infusion; and 30 minutes, 1 hour, and 2 hours following completion of the infusion.
- c. **Pulse oximetry**: On Days 0, 7, 14, 21, and 28, pulse oximetry to be measured immediately prior to the infusion; 15, 30, and 45 minutes after the start of the infusion; at completion of the infusion; and 30 minutes, 1 hour and 2 hours following completion of the infusion.
- d. **Clinical safety labs**: hematology, clinical chemistry, and urinalysis (see [Section 7.5](#) for a complete list). Full clinical safety laboratory draws will be collected at screening and on Days 0, 7, 14, 21, 28, 33, 42, 56, 84, and 112.
- e. **Pregnancy test (women of childbearing potential only)**: To be performed at time of screening, prior to first dose of SYNT001 on Day 0, and on Days 56 and 112. Urine or serum test is acceptable; however, positive urine tests must be confirmed with serum testing.
- f. Digital 12-lead **ECG** to be obtained in triplicate at least 1 to 2 minutes apart and after 5 minutes of rest in a supine position. See [Section 7.6](#) for additional information. On Days 0 and 28 to be obtained 5 minutes after the completion of infusion. Day 12 ECG will be collected only if the visit is conducted at the study site.
- g. **Serology**: Testing at Day 56 will not be done for any subject whose baseline titer is below the level of detection. If the Day 56 results are greater than 30% below the baseline value, or if the subject falls below the level of detection, the subject will be re-tested at Day 84; if still below the baseline value (or level of detection), the subject will be re-tested at Day 112. Any subject whose baseline value for tetanus or VZV was above the detectable level at baseline, and is not within 30% of the baseline value or is below the detectable level by Day 112, will be referred to their primary care physician for further management. See [Section 7.5.3](#) for additional information.
- h. **PK**: Starting on Days 0 and 28, serum samples will be collected just prior to the start of study drug infusion (pre-dose), and at 5 minutes and 2, 4, 6, 24, and 48 hours after the end-of-study drug infusion. Additional samples will be collected on Days 5 and 33. See [Section 7.5.4](#) for additional information.
- i. **Immunogenicity**: Samples will be collected pre-dose when collected on dosing days. Samples will be collected on Days 0, 14, 28, 56, 84 and 112. See [Section 7.5.6](#) for additional information.
- j. Prior to **study drug infusion**, SYNT001 drug product is to be diluted in dextrose 5% in water (D5W) to a total volume of 250 mL and administered intravenously over 1 hour using a 0.2-micron inline filter. See [Section 4](#) and [Section 7.8](#) for additional information.
- k. **Immunoglobulins (IgG, IgA, IgM) and IgG subtypes (IgG1-4)**: Collected for measurements of IgG, IgG subtypes (IgG1-4), IgA, IgM at every visit. On Days 0, 7, 14, 21, and 28, samples are collected prior to infusion of study drug. See [Section 7.5.5](#) for additional information.
- l. **Exploratory pharmacodynamic samples (C3 and AECA)**: Collected pre-dose when collected on dosing days. See [Section 7.5.5](#) for complete information.
- m. Buccal samples to be collected and stored; pending review of clinical and pharmacodynamics assessments.
- n. Immunophenotyping by flow cytometry for measurement of CD3+CD4+ T, CD3+CD8+ T, monocytes, NK cells and B cells.
- o. Photographs of active lesions taken prior to first dose on Day 0. Follow-up photographs will be taken at Days 33, 56, 84 and 112. Subjects who begin a steroid taper will have additional photographs taken at the clinic visit during which the decision to begin the taper is made.
- p. Visit Days 5, 12, and 19 may be conducted via at-home nurse in lieu of a subject visit to the study site.
- q. Subjects will return to the clinic on Days 84 and 112 for follow-up visits. Subjects whose total IgG is not within 30% of their Day 0 baseline value and not above 500 mg/dL at the Day 112 visit will be referred for further management.

**Table 3. Study Assessment for Cohort 2**

Visit Number	Screening	Loading			Maintenance					Follow-Up		
	1	2	3	4	5	6	7	8	9	10	11	12
Time Point (Study Day)	-14 to -1	0 Baseline	7 (±1 d)	14 (±1 d)	28 (±3 d)	42 (±3 d)	56 (±3 d)	70 (±3 d)	84 (±3 d)	91 (±5 d) or ET visit	112 (±5 d)	140 (±5 d) EOS
Informed consent	X											
Demographics/medical history	X											
Inclusion/exclusion	X											
Physical examination a	X	X	X	X	X	X	X	X	X	X		X
Vital signs b	X	X	X	X	X	X	X	X	X	X	X	X
Pulse oximetry c		X	X	X	X	X	X	X	X			
Clinical safety labs d	X	X	X	X	X	X	X	X	X	X	X	X
Pregnancy test e	X	X			X					X		X
Hepatitis and HIV screen	X											
12-lead ECG f	X	X		X	X					X		X
Tetanus and VZV antibodies g		X			X					X		X
PDAI h	X	X	X	X	X	X	X	X	X	X	X	X
PK sampling i		X	X	X	X				X			
Immunogenicity j	X	X	X	X	X	X	X	X	X	X	X	X
Study drug administration k		X	X	X	X	X	X	X	X			
Immunoglobulins (IgG, IgA, IgM) and IgG subtypes (IgG1-4) l	X	X	X	X	X	X	X	X	X	X	X	X q
CIC		X	X	X	X	X	X	X	X	X	X	X
Anti-Dsg (1 and 3) antibody titers	X	X	X	X	X	X	X	X	X	X	X	X
C3 and AECA m	X	X	X	X	X	X	X	X	X	X	X	X
FCGR2A by buccal swab n		X										
RNA sequencing		X			X					X		
Immunophenotyping o		X			X					X		
Exploratory pemphigus immune response biomarkers		X	X	X	X	X	X	X	X	X	X	X
Photography p		X	X	X	X	X	X	X	X	X	X	X
HR-QoL assessments		X			X					X		X

Adverse events	To be collected from the date that the ICF is signed through the last study visit
Concomitant medications	To be collected from within 14 days prior to Day 0 through the last study visit

Abbreviations: CIC = circulating immune complexes; d = day(s); ECG = electrocardiogram; EOS = end of study; ET= early termination; FcGR2a= Fc gamma R2a receptor; HIV = human immunodeficiency virus; HR-QoL = health-related quality of life; ICF = informed consent form; Ig = immunoglobulin; PDAI = Pemphigus Disease Area Index; PK = pharmacokinetic; VZV = varicella-zoster virus

- a. Complete **physical examination**, including weight, to be performed. Height and body mass index will be additional assessments conducted at screening only.
- b. **Vital sign** measurements (sitting blood pressure, heart rate, respiratory rate, and oral temperature) to be obtained after 5 minutes of seated rest. Any abnormal measurements are to be repeated after 5 minutes of rest. Vital sign measurements will be taken on all study visits. On dosing days, vital sign measurements will be collected immediately prior to the infusion; 15, 30, and 45 minutes after the start of the infusion; at completion of the infusion; and 30 minutes, 1 hour and 2 hours following completion of the infusion.
- c. **Pulse oximetry**: On dosing days, pulse oximetry to be measured immediately prior to the infusion; 15, 30, and 45 minutes after the start of the infusion; at completion of the infusion; and 30 minutes, 1 hour, and 2 hours following completion of the infusion.
- d. **Clinical safety labs**: hematology, clinical chemistry, and urinalysis. See [Section 7.5](#) for a complete list. Full clinical safety lab draws will be collected at screening and at all study visits prior to infusion if applicable.
- e. **Pregnancy test (women of childbearing potential only)**: To be performed at time of screening and prior to dose on dosing days if applicable. Urine or serum test is acceptable; however, positive urine tests must be confirmed with serum testing.
- f. Digital 12-lead **ECG** to be obtained after 5 minutes of rest in the supine position and in triplicate approximately 1 minute apart. See [Section 7.6](#) for additional information. On days of treatment, to be obtained approximately 5 minutes after the completion of infusion.
- g. **Serology**: Any subject whose baseline value for tetanus or VZV was above the protective level at baseline and is not within 30% of the baseline value or is below the protective level by End of Follow-up, will be referred to their primary care physician for further management. See [Section 7.5.3](#) for additional information.
- h. PDAI will be administered at screening. Subject eligibility requires a PDAI total activity score >4. Thereafter, assuming eligibility, the PDAI will be administered during Treatment Period and Follow-up Period. See [Section 7.7](#) for additional information.
- i. **PK**: Starting on dosing days, serum samples will be collected just prior to the start of study drug infusion (pre-dose) and at 5 minutes, 1 and 2 hours after the end of study drug infusion. See [Section 7.5.4](#) for additional information.
- j. **Immunogenicity**: Samples will be collected pre-dose when collected on dosing days. See [Section 7.5.6](#) for additional information
- k. Prior to **study drug infusion**, SYNT001 drug product is to be diluted in dextrose 5% in water to a total volume of 250 mL and administered intravenously over 1 hour ±15 minutes using a 0.2-micron, inline filter. See [Section 4](#) for additional information.
- l. **Immunoglobulins (IgG, IgA, IgM) and IgG subtypes (IgG 1-4)**: Collected for measurements of IgG, IgG subtypes (IgG1-4), IgA, and IgM at every visit. On dosing days, samples are collected prior to infusion of study drug. See [Section 7.5.5](#) for additional information.
- m. Exploratory pharmacodynamic samples (C3 and AECA): Collected pre-dose when collected on dosing days. See [Section 7.5.5](#) for complete information.
- n. Buccal samples to be collected pre-dose.
- o. **Immunophenotyping** by flow cytometry for measurement of CD3+CD4+ T, CD3+CD8+ T, monocytes, natural killer (NK) cells, and B cells. Collect samples pre-dose on dosing days.
- p. Photographs of all active lesions taken pre-dose on dosing days. Subjects who begin a steroid taper will have additional photographs taken at the clinic visit during which the decision to begin the taper is made.
- q. Subjects whose total IgG is not within 30% of their Day 0 baseline value and not above 500 mg/dL at the Day 140 visit will be referred for further management.

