#### **8.4 All Cohorts: End of Study or Early Termination Visit; Cohort 1, Day 112; Cohort 2, Days 91 and 140**

For Cohort 1 Day 112 ( $\pm 5$  days) and Cohort 2 Days 91 and 140 ( $\pm 5$  days), subjects are to return to the clinic and the following procedures are to be performed:

- Complete physical exam
- Vital sign measurements (after 5 minutes of rest; sitting blood pressure, heart rate, respiratory rate, oral temperature): abnormal results to be repeated after 5 minutes of rest
- Clinical safety laboratory tests (hematology, serum chemistry panel, urinalysis)
- Pregnancy test
- 12-lead ECG (to be obtained in triplicate after 5 minutes of rest in the supine position) (*Cohort 2, Days 91 and 140 only*)
- Serum tetanus antibody and VZV antibody
- PDAI
- Immunogenicity sample collection
- PD sample collection
  - IgG, IgG subtypes (IgG1-4), IgA, IgM
  - CIC
  - Anti-Dsg (1 and 3) antibody titers
  - C3
  - AECA
  - RNAseq (*Cohort 1 Day 112; Cohort 2, Day 91 only*)
  - Urine IgG (*Cohort 1 only*)
  - Immunophenotyping (*Cohort 2, Day 91 only*)
  - Exploratory pemphigus immune response biomarkers
- Photography
- HR-QoL (ABQoL, Skindex-29) (*Cohort 2 only*)
- Concomitant medication assessment
- AE assessment

**Note:** a subject may choose to terminate participation in the study at any time. Under this circumstance, the subject will be encouraged to return as soon as possible for an early termination visit and to receive assessments otherwise scheduled on Day 112 (Cohort 1) or Day 91 (Cohort 2).

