## **9. STUDY RULES**

### **9.1 Subject Withdrawal**

Every reasonable effort will be made to keep the subject in the study; however, if a subject withdraws from the study, the Investigator should complete and report the reasons for withdrawal as thoroughly as possible. The reason(s) for termination must be clearly documented on the appropriate page of the eCRF.

Subjects who have received at least one SYNT001 dose and withdraw or prematurely discontinue study drug should be encouraged to attend, at a minimum, the early termination (ET) visit Day 112 (Cohort 1) or Day 91 (Cohort 2). Subjects in Cohort 2 will also be encouraged to attend the remaining follow up visits on Days 112 and 140.

If the subject fails to return for these assessments for unknown reasons, every effort (eg, telephone, email, and letter) should be made to contact them.

The reason(s) for a subject's participation in the study may be prematurely discontinued will be documented and include:

1. The subject wishes to withdraw from the study.
2. Request by a regulatory agency or Institutional Review Board).
3. The subject experiences a significant or intolerable AE.
4. The subject experiences a significant adverse change in vital signs, physical examination findings, or clinical laboratory parameter.
5. The subject has a need for a concomitant medication that is not permitted by the study protocol.
6. The subject experiences generalized impairment or mental incompetence that would result in the subject being unable to understand his or her participation in the study.
7. If, in the Investigator's medical judgment, further participation would be injurious to the health and well-being of the subject, or is not in the best interest of the subject.
8. Administrative reasons, such as subject non-compliance or a major protocol violation.

If at the discretion of the Investigator with consultation with the Medical Monitor, a subject requires a significant increase in dose(s) of anti-pemphigus medication(s) for the management of pemphigus, the subject should be encouraged to attend, at a minimum, the ET visit Day 112 (Cohort 1) or Day 91 (Cohort 2). Subjects in Cohort 2 will also be encouraged to attend the remaining follow up visits on Days 112 and 140.

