#### **10.5 Other Safety Considerations**

##### **10.5.1 Laboratory Data**

All laboratory data obtained during the study should be reviewed. Any abnormal value that leads to a change in subject management (eg, requirement for additional medication or monitoring) or is determined to be of clinical significance by the Investigator should be reported as an AE and/or SAE as appropriate, unless this value is consistent with values obtained before entry into the study.

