**APPENDIX 5. COHORT 2 ALTERNATE SCHEDULE OF EVENTS TABLE**

**Table 10. Study Assessments for Cohort 2 (Alternate Weekly Dosing Option)**

Visit Number	Screening	Loading			Maintenance										Follow-Up		
	1	2	3	4	5	6	7	8	9	10	11	12	13	14	15	16	17
Time Point (Study Day)	-14 to -1	0 Baseline	7 (±1 d)	14 (±1 d)	21 (±3 d)	28 (±3 d)	35 (±3 d)	42 (±3 d)	49 (±3 d)	56 (±3 d)	63 (±3 d)	70 (±3 d)	77 (±3 d)	84 (±3 d)	91 (±5 d) or ET Visit	112 (±5 d)	140 (±5 d) EOS Visit
Informed consent	X																
Demographics/medical history	X																
Inclusion/exclusion	X																
Physical examination a	X	X	X	X	X	X	X	X	X	X	X	X	X	X	X		X
Vital signs b	X	X	X	X	X	X	X	X	X	X	X	X	X	X	X	X	X
Pulse oximetry c		X	X	X	X	X	X	X	X	X	X	X	X	X			
Clinical safety labs d	X	X	X	X	X	X	X	X	X	X	X	X	X	X	X	X	X
Pregnancy test e	X	X			X										X		X
Hepatitis and HIV screen	X																
12-lead ECG f	X	X		X	X										X		X
Tetanus and VZV antibodies g		X			X										X		X
PDAI h	X	X	X	X	X	X	X	X	X	X	X	X	X	X	X	X	X
PK sampling i		X	X	X	X		X							X			
Immunogenicity j	X	X	X	X	X	X	X	X	X	X	X	X	X	X	X	X	X
Study drug administration k		X	X	X	X	X	X	X	X	X	X	X	X	X			
Immunoglobulins (IgG, IgA, IgM) and IgG subtypes (IgG1-4) l	X	X	X	X	X	X	X	X	X	X	X	X	X	X	X	X	X q
CIC		X	X	X	X	X	X	X	X	X	X	X	X	X	X	X	X
Anti-Dsg (1 and 3) antibody titers	X	X	X	X	X	X	X	X	X	X	X	X	X	X	X	X	X
C3 and AECA m	X	X	X	X	X	X	X	X	X	X	X	X	X	X	X	X	X
FCGR2A by buccal swab n		X															
RNA sequencing		X			X										X		
Immunophenotyping o		X			X										X		
Exploratory pemphigus immune response biomarkers		X	X	X	X	X	X	X	X	X	X	X	X	X	X	X	X

Photography p		X	X	X	X	X	X	X	X	X	X	X	X	X	X	X	X
HR-QoL assessments		X			X											X	X
Adverse events	To be collected from the date that the ICF is signed through the last study visit																
Concomitant medications	To be collected from within 14 days prior to Day 0 through the last study visit																

CIC = circulating immune complexes; d = day(s); ECG = electrocardiogram; EOS = end of study; ET= early termination; *FCGR2A* = Fc gamma R2a receptor; HIV = human immunodeficiency virus; HR-QoL = health-related quality of life; ICF = informed consent form; Ig = immunoglobulin; PDAI = Pemphigus Disease Area Index; PK = pharmacokinetic; VZV = varicella-zoster virus

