- i. **PK**: On dosing days if applicable, serum samples will be collected just prior to the start of study drug infusion (pre-dose) and at 5 minutes, 1 and 2 hours after the end of study drug infusion. See [Section 7.5.4](#) for additional information.
- j. **Immunogenicity**: Samples will be collected pre-dose when collected on dosing days. See [Section 7.5.6](#) for additional information.
- k. Prior to **study drug infusion**, SYNT001 drug product is to be diluted in dextrose 5% in water to a total volume of 250 mL and administered intravenously over 1 hour ±15 minutes using a 0.2-micron, inline filter. See [Section 4](#) for additional information.
- l. **Immunoglobulins (IgG, IgA, IgM) and IgG subtypes (IgG 1-4)**: Collected for measurements of IgG, IgG subtypes (IgG1-4), IgA, and IgM at every visit. On dosing days, samples are collected prior to infusion of study drug. See [Section 7.5.5](#) for additional information.
- m. Exploratory pharmacodynamic samples (C3 and AECA): Collected pre-dose when collected on dosing days. See [Section 7.5.5](#) for complete information.
- n. Buccal samples to be collected pre-dose.
- o. **Immunophenotyping** by flow cytometry for measurement of CD3+CD4+ T, CD3+CD8+ T, monocytes, natural killer (NK) cells, and B cells. Collect samples pre-dose on dosing days.
- p. Photographs of all active lesions taken pre-dose on dosing days. Subjects who begin a steroid taper will have additional photographs taken at the clinic visit during which the decision to begin the taper is made.
- q. Subjects whose total IgG is not within 30% of their Day 0 baseline value and not above 500 mg/dL at Day 140 will be referred for further management.

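### Cohort 2's only written IgG referral threshold applies at Day 140, so a subject whose final visit is ET/Day 91 or Day 112 has IgG measured but no referral rule applied

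*Protocol*

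**What the plan says.** Both Cohort 2 schedules attach marker q to one cell only, total IgG at Day 140. Footnote q of Table 3 refers subjects whose IgG is "not within 30% of their Day 0 baseline value and not above 500 mg/dL at the Day 140 visit will be referred". Table 10, the alternate weekly schedule, refers those "not above 500 mg/dL at Day 140 will be referred for further management". Both parts of the criterion must be met.

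IgG is drawn at every Cohort 2 visit. The ET visit is not in the Day 140 column. It is headed "91 (±5 d) or ET visit" in Table 3 and "91 (±5 d) or ET Visit" in Table 10, and the IgG cell there has a plain X.

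Under Section 8.4 a subject who stops early is "encouraged to return as soon as possible for an early termination visit" and in Cohort 2 receives the Day 91 assessments. Section 9.1 makes ET the minimum visit to aim for, and adds: "Subjects in Cohort 2 will also be encouraged to attend the remaining follow up visits on Days 112 and 140".

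In Cohort 1 (Table 2), Day 112 and ET share one column. The referral footnote there covers subjects "not above 500 mg/dL at the Day 112 visit will be referred for further management".

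Other provisions bear on a low IgG without setting a referral threshold:
- The synopsis (study design) has the Medical Monitor and the Sponsor Medical Lead review PD data, including IgG, throughout the study.
- Under Section 10.5.1, a laboratory value that changes management or "is determined to be of clinical significance by the Investigator should be reported as an AE and/or SAE as appropriate", unless it matches values from before entry.
- Section 10.2.4 requires follow-up of anything reported as an AE. Sections 7.11 and 9.5.3 require follow-up of subjects who leave because of an AE.

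**The concern.** Section 10.3.3 acknowledges that repeated dosing can take IgG into the range of primary humoral immunodeficiency. Part of its justification for accepting this is that the low levels will be temporary. Footnote q is the one written IgG criterion that checks whether they were.

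A subject who completes the study with a low Day 91 value needs no referral then, because IgG is sampled again at Days 112 and 140. A subject who will not come back has no later study sample, and the protocol does not say what to do with the value in hand.

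Early exit is foreseen. Section 10.3.2 stops treatment after any Grade 2 or higher infusion reaction. Section 9.1 lists the need for a non-permitted medication as a reason for leaving, and Section 7.12 counts rituximab and immunosuppressants outside the permitted list among those. Some early leavers could therefore have low IgG while starting further immunosuppression.

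The stake is safety follow-up of individual subjects. No endpoint or analysis is affected.

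**Working it through.** **Coverage in Cohort 2, visit by visit**

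| Final visit attended | Days after planned last dose (Day 84) | IgG drawn | Footnote q applied |
|---|---|---|---|
| ET / planned Day 91 | 91 − 84 = 7 (Day 91; ET may fall at any time) | yes | no |
| Day 112 | 112 − 84 = 28 | yes | no |
| Day 140 | 140 − 84 = 56 | yes | yes |

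No other section supplies an IgG threshold. Section 7.5.3 covers tetanus and VZV antibodies. Section 7.5.5 covers sampling. Section 10.3.3 covers clinical monitoring for infection and possible IVIG. Section 10.5.1 is a general rule. IgG is not in the safety panel of Table 6, and the Investigations list in Appendix 1 has no specific immunoglobulin term, so no toxicity grade prompts action either.

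**Could an early leaver meet the criteria?**

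Inputs:
- Minimum screening IgG of 600 mg/dL (exclusion criterion 12).
- Mean normal IgG of 1150 mg/dL (Section 10.3.3).
- Modelled reduction of 50% to 68% in maintenance and about 78% at the nadir, Days 21 to 28 (Section 2.2).
- Observed mean reduction of 59% in Cohort 1 (Section 2.2).

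Formula: level = baseline × (1 − reduction). Footnote q is met when the reduction exceeds 30% and the level is 500 mg/dL or less.

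The plan's own figures in Section 10.3.3 reproduce. At 50%, 1150 × 0.50 = 575 and 600 × 0.50 = 300. At 80%, 1150 × 0.20 = 230 and 600 × 0.20 = 120.

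Every reduction considered exceeds 30%, so the 500 mg/dL part decides:
- Baseline 600: 600 × 0.50 = 300, 600 × 0.32 = 192 and 600 × 0.22 = 132. Met throughout.
- Baseline 1150: 1150 × 0.50 = 575, not met. 1150 × 0.41 = 471.5, 1150 × 0.32 = 368 and 1150 × 0.22 = 253, all met. The switch is at 1 − 500/1150 = 56.5%.
- Highest baseline that meets the rule: 500/0.50 = 1000 at 50%, 500/0.41 ≈ 1220 at 59%, 500/0.32 = 1562.5 at 68% and 500/0.22 ≈ 2273 at 78%.

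A subject who leaves during or soon after treatment could readily meet the sponsor's own criteria.

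**The case against.** **The cohorts do not contradict each other.** A reader might infer from the shared Day 112/ET column in Table 2 that Cohort 1 refers early leavers and Cohort 2 does not. The wording does not support that. Cohort 1's footnote q also names only its scheduled final day, so all three footnotes apply one rule at the planned end of study. This objection stands, and the point is about coverage only.

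**Early leavers are not unwatched.** A reader might also infer that nobody follows their IgG. The documents do not support that either. IgG is reviewed centrally as the study runs, investigators must review laboratory data, AEs are followed, and Section 9.4 requires repeated contact attempts and then a registered letter. The tetanus and VZV tests are drawn in the ET column and carry their own referral. That rule is tied to the end of follow-up or end-of-study visit and tests specific antibodies, not total IgG. These provisions narrow the gap, but none tells anyone to refer a departing subject at a stated IgG level. A 60% to 90% fall is the dose-selection target, so a low value may fairly be read as intended pharmacology and not reported as an AE.

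**The rule tests recovery, and ET may be too early for that.** At a 68% reduction it is met up to about 1562 mg/dL, nearly all of the 500 to 1600 mg/dL range in Section 10.3.3. At ET it would often flag the drug effect and not a failure to recover. This stands as a cost of the change. It does not remove the case for a handover when no later sample will be taken.

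**Conclusion.** The point holds as a minor patient-safety improvement. Followed exactly, the protocol lets a Cohort 2 subject finish at ET/Day 91 or Day 112 with IgG in a range it likens to primary humoral immunodeficiency, and applies no referral rule. The text of Tables 3 and 10 and Sections 8.4 and 9.1 is enough to establish this.

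The number affected is unknown. It is some part of a planned maximum of 12, with replacement of certain withdrawals allowed under Section 9.2. The levels shown rest on the sponsor's model and on two example baselines. They are not a forecast, because the timing of early exits is not known. Recovery is expected: Section 2.2 reports return to baseline within 1 to 2 months after five 10 mg/kg doses. The protocol reports no observed human recovery after the Cohort 2 loading regimen.

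**What to change.** In footnote q of Tables 3 and 10, replace the reference to Day 140 with: *at the Day 140 visit or, for a subject who will not attend Day 140, at the ET/Day 91 or Day 112 visit, whichever is the last follow-up visit attended*. Add marker q to the IgG cells of the Day 91/ET and Day 112 columns. If a subject is lost after one of these visits, the value is on file and the rule can be applied once the loss is clear.

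Do not extend the threshold to dosing visits. Footnote l has IgG drawn before the infusion on those days, so the value predates the dose just given, and at Day 0 it is the baseline itself. A subject who was dosed and attends no follow-up visit should instead be referred for an IgG check when contacted under Section 9.1 or 9.4. One added sentence covers both points.

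The thresholds, study visits and scheduled samples do not change, and subjects who attend Day 140 are handled as now. The cost is a short text change in two tables, plus referrals for many early leavers whose IgG is low from recent dosing and expected to recover.
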